5.3 Compliance

Compliance with Lapatinib and Veliparib will be evaluated by a physical pill count at the scheduled clinic visits on Weeks 4, 8, 12, 16, 20, and 24. Patients will be instructed to bring their used bottles of Lapatinib and Veliparib to each return visit, along with any unused tablets. The investigator/designee will count the number of remaining tablets at each visit to assess compliance. In the event that the patient forgets to bring their used study meds to their clinic visit, compliance will be assessed by direct questioning of the subject. In this case, patients should be counseled to bring their used drug bottles to their next scheduled appointment so that compliance may be confirmed by pill count. Patients should be instructed to report any missed doses of either Lapatinib or Veliparib to the study coordinator.

Compliance with Lapatinib and Veliparib will be calculated by the ratio of number of pills actually taken to the number of pills that should have been taken. Compliance will be defined as a ratio ≥ 0.75 . Subjects with ratios between 1.00 and 0.75 will be allowed to continue on study. Study staff should ensure patient understanding of dosing instructions for patients whose compliance is less than 100%. In addition, the importance of compliance with anticancer therapy should be reinforced. Patients found to be in less than 75% compliance on more than one occasion will be taken off study for non-compliance. Subjects who miss doses as a result of physician prescribed drug holidays will not be considered non-compliant. Calculation of the compliance ratio should thus be adjusted such that the “number of pills that should have been taken” reflects the drug holiday.

6.0 TREATMENT PLAN

6.1 Introduction

Patients with pathologically confirmed TNBC (estrogen receptor negative, progesterone receptor negative, HER-2-Neu negative – see definitions in section 4.2) who have metastatic disease and have not been treated previously for metastatic disease (but received anthracyclines and taxanes in the adjuvant or neoadjuvant settings) or have failed one or more chemotherapy regimens in the metastatic setting (anthracyclines and taxanes) will be offered participation in this trial with appropriate informed consent. It is mandatory for the patients enrolled in the trial to have a biopsy of one of the metastatic lesions before they will be treated with the research schema (see eligibility

criteria) if biopsy sites are appropriate; patient advocates will play a very important role in this task of the protocol. Patients with NO reasonably accessible lesions as described above can be enrolled in the trial.

6.2 Pilot Trial

Twenty patients evaluable for response will be entered into this phase pilot trial; they will receive Lapatinib (1250 mg a day continuously for 28 days) in combination with Veliparib 200 mg every 12 hours for 28 consecutive days, starting on Day 2 Cycle 1). No blinding will be used in this study. Patients will be evaluated for response every 2 courses (every 8 weeks) according to the RECIST criteria version 1.1 (see Appendix D). Treatment will be administered on an outpatient basis. Treatment may continue without interruption in patients with CR, PR or SD until progression of the disease or unacceptable toxicity. Patients cannot receive any other concomitant therapy: chemotherapy, targeted therapy, radiation therapy, or other investigational agent while participating in the study. There are some restrictions on concomitant medications which must be recorded (see Appendix H). Patients may receive bisphosphonates; however, if used, bone lesions may not be used for progression or response. Patient with PD at any time will be taken off the study.

Investigators will maintain a confidential screening log of all potential study candidates that includes limited information about the patients (initials, sex, age), date, and outcome of screening process: enrolled in the study, reason for ineligibility or refused to participate. Investigators will be expected to maintain an enrollment log for all patients enrolled in the study indicating their assigned study number. A patient will be considered enrolled upon assignment of a patient number. Each patient will sign an informed consent provided by the site.

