6.2.2 Pre-study Assessments

Informed consent will be obtained before study-specific screening evaluations are performed. Screening evaluations must be performed within 4 weeks prior to day 0.

Within the 4 weeks prior to therapy initiation patients will undergo baseline clinical evaluation (including history, physical evaluation, vital signs, and performance status) and all enrolled patients will undergo biopsy of a selected lesion according to the guidelines described in eligibility criteria. Additional pre-study evaluations include: CBC with differential and platelets, CMP (fasting), CA27.29, pregnancy test (within 7 days if indicated), tumor measurements by images or staging studies which are defined as studies contributing to response evaluation, e.g. CTs (chest, abdomen, and pelvis), MRI, bone scan, PET, or plain x-rays, EKG and echocardiogram, and concomitant medication assessment. The ejection fraction will be confirmed as normal before proceeding with the first dose of lapatinib.

Patients with reasonably accessible lesions as described above, who will not agree with the biopsy, will not be enrolled in the trial. Patients with NO reasonably accessible lesions as described above can be enrolled in the trial.

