6.7.1 Definitions

Measurable Disease – Measurable lesions are defined as those that can be accurately measured in at least one dimension (longest diameter to be recorded) as ≥ 20 mm by chest x-ray, as ≥ 10 mm with CT scan, or ≥ 10 mm with calipers by clinical exam. All tumor measurements must be recorded in millimeters (or decimal fractions of centimeters).

Definitions proved for normal: short axis < 10 mm, Measurable (Target): short axis ≥ 15 mm, Non-measurable: short axis 10 to <15 mm, Target nodes measured in the short axis (perpendicular to longest diameter) more reproducible and predictive of malignancy. Short axes of target nodes to be added to the sum of longest diameters.

Non-Measurable Disease – All other lesions (or sites of disease), including small lesions (longest diameter <10 mm or pathological lymph nodes with >10 to <15 mm short axis, are considered non-measurable disease. Bone lesions, leptomeningeal disease, ascites, pleural/pericardial effusions, lymphangitis cutis/pulmonitis, inflammatory breast disease, and abdominal masses (not followed by CT or MRI), are considered as non-measurable

Target Lesions – All measurable lesions up to a maximum of two lesions per organ and 5 lesions in total, representative of all involved organs, should be identified as target lesions and recorded and measured at baseline. Target lesions should be selected on the basis of their size (lesions with the longest diameter), be representative of all involved organs, but in addition should be those that lends themselves to reproducible repeated measurements. It may be the case that, on occasion, the largest lesion does not lend itself to reproducible measurement in which circumstance the next largest lesion which can be measured reproducibly should be selected. A sum of the diameters (longest for non-nodal lesions, short axis for nodal lesions) for all target lesions will be calculated and reported as the baseline sum. If lymph nodes are to be included in the sum, then only the short axis is added to the sum. The baseline sum LD will be used as referenced by which to characterize the objective tumor response.

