6.7.3 Response Criteria

6.7.3.1 Evaluation of Target Lesions

- **Complete Response (CR):** Disappearance of all target lesions. Any pathological lymph nodes (whether target or not) must have reduction in short axis to < 10mm.
- **Partial Response (PR):** At least a 30% decrease in the sum of the longest diameter (LD) of target lesions, taking as reference the baseline sum diameters.
- **Progressive Disease (PD):** At least a 20% increase in the sum of the diameters of target lesions, taking as reference the smallest sum on study (this included the baseline sum if that is the smallest on study). In addition to the relative increase of 20%, the sum must also demonstrate an absolute increase of at least 5mm. (Note: the appearance of one or more new lesions is also considered progression.)
- **Stable Disease (SD):** Neither sufficient shrinkage to qualify for PR nor sufficient increase to qualify for PD, taking as reference the smallest sum diameters while on study.

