6.7.3.2 Evaluation of Non-Target Lesions

- **Complete Response (CR):** Disappearance of all non-target lesions and normalization of tumor marker level. All lymph nodes must be non-pathological in size (<10mm short axis). Note: If serum CA27.29 levels are initially above the upper normal limit, they must normalize for a patient to be considered in complete clinical response.
- **Non-CR/Non-PD:** Persistence of one or more non-target lesion(s) and/or maintenance of tumor marker level above the normal limits.
- **Progressive Disease (PD):** Appearance of one or more new lesions and/or unequivocal progression of existing non-target lesions. Unequivocal progression should not normally trump target lesion status. It must be representative of overall disease status change, not a single lesion increase.
Although a clear progression of “non-target” lesions only is exceptional, in such circumstances the opinion of the treating physician should prevail, and the progression status should be confirmed at a later time by the review panel (or study chair).

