6.7.6 Definitions Related to Evaluation Unrelated to Objective Response

Overall Survival is the observed length of life from entry into the study to death or the date of last contact.

Progression-Free Survival is the period from study entry until disease progression, or death, whichever occurs first.

Recurrence-Free Survival (non-measurable disease studies) is the period from study entry until disease recurrence, death or date of last contact.

Subjective Parameters including performance status, specific symptoms, and side effects.

Side effects are graded according to the National Cancer Institute (NCI) Common Terminology Criteria for Adverse Events (CTCAE) version 4.03 (see Appendix A). Any patient who receives treatment on this protocol will be evaluated for toxicity. Each patient will be assessed periodically according to the study parameters table for the development of any toxicity. Dose modifications will be made based on toxicities as described earlier.

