7.5.2 Analysis of Efficacy endpoints

At the completion of the study, the secondary endpoint of ORR rate will be estimated along with two-sided 95% confidential intervals for Lapatinib and Veliparib combination group with exact method of [Clopper-Pearson intervals](#). Secondary endpoint analysis will be descriptive. Mean, median, and range will be used to describe continuous demographic variables. Frequency and proportion will be used to describe categorical variables. The K-M estimator will be used to estimate median progression free survival along with 95% confidence intervals.

Exploratory analysis will be conducted on the correlations between clinical outcomes and biomarkers or gene expression profiles. Gene expression profile, proliferation/apoptosis markers, and circulating level of tumor cells will be analyzed between responders and non-responders using two-sample t-test test assuming normal distribution for gene expression level. An appropriate normal transformation will be conducted prior analysis when it is necessary. Alternatively, one way analysis of variance (ANOVA) can be used to evaluate gene expression and biomarkers by responders. Logistic regression analysis will be used to predict response with these genes or biomarkers with or without adjustment for covariate, e.g. age. Two-sample log rank test will be used to compare PFS curves classified by biomarkers or gene expression profiles so that potential prognostic biomarkers or genes will be identified. Multivariate Cox proportional hazards model will be used to identify a set of biomarkers for prediction of time to disease progression between responders and non-responders. Hazards ratios with 95% confidence intervals will be calculated for each significant biomarker in terms of predicting time to disease progression. Since this is an exploratory pilot study which will be used as a hypothesis generator. We will include EGFR expression and location, and markers of apoptosis and DNA repair as covariate in all above

exploratory analysis.

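### For bisphosphonate users, sections 4.1 and 6.2 bar bone lesions from progression and response, while 6.7.3–6.7.4 count every new lesion as progression; nothing says which rule defines PFS and ORR

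*Combined protocol and SAP*

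**What the plan says.** The bisphosphonate rule stands in 4.1 (Inclusion Criteria) and in 6.2 (Pilot Trial) in the same words: "Patients may receive bisphosphonates; however, if used, bone lesions may not be used for progression or response".

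The response criteria contain no such exclusion. For target disease, 6.7.3.1 notes that "the appearance of one or more new lesions is also considered progression". For non-target disease, 6.7.3.2 defines progression as "Appearance of one or more new lesions and/or unequivocal progression of existing non-target lesions". The table in 6.7.4 assigns PD whenever there is a new lesion, whatever the target and non-target status. Section 6.7.1 begins its list of non-measurable sites with "Bone lesions, leptomeningeal disease, ascites, pleural/pericardial effusions", so bone disease is followed as non-target disease.

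On the endpoints, 6.7.6 says "Progression-Free Survival is the period from study entry until disease progression, or death, whichever occurs first", and 7.5.2 says "The K-M estimator will be used to estimate median progression free survival along with 95% confidence intervals". ORR is estimated with an exact 95% interval, and 7.4 makes a response rate of 30% or more the condition for proposing a phase II trial. Progression also has a treatment consequence in 6.2: "Patient with PD at any time will be taken off the study".

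**The concern.** Two rules apply to the same event. Take a bisphosphonate user whose scan shows a new bone metastasis and nothing else new. Under 6.7.3–6.7.4 that scan is the date of progression. Under 4.1 and 6.2 it is not an event, and PFS runs on to a later progression, death or censoring. PFS is defined through disease progression without saying which rule decides it.

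The condition on bisphosphonate use also has no time limit. Read literally, a bisphosphonate started because a bone lesion has appeared would make that lesion uncountable. Ascertainment of the endpoint would then depend on a concomitant drug begun after enrolment, in an open-label trial with no control arm in which the same distortion could cancel.

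At stake are the two main efficacy summaries, PFS and ORR, and the exploratory biomarker analyses in 7.5.2 that use them as outcomes.

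**Working it through.** **1. The rules side by side, for a bisphosphonate user**

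| Finding | 4.1 and 6.2, literally | 6.7.3–6.7.4 |
|---|---|---|
| New bone lesion only | Not progression | PD |
| Unequivocal progression of an existing bone lesion | Not progression | PD (non-target) |
| PR in target lesions plus a new bone lesion | PR | PD |

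No section gives an order of precedence.

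**2. Direction**

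Under 6.7.3 a patient's PFS time is the earliest of all progression types and death. Under the literal 6.2 rule it is the earliest of a subset of these. The minimum over a subset cannot be smaller, so each patient's recorded time is the same or later. In a simulation of 400,000 patients per scenario, none had a shorter time.

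ORR also moves one way only. Bone lesions are non-measurable under 6.7.1, so they cannot supply a PR themselves. Ignoring them can only keep a patient as a responder who would otherwise be PD at or before the scan at which PR is reached.

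**3. ORR**

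One patient is 1/20 = 5 percentage points. The threshold in 7.4 is 30%, or 6/20; 5/20 is 25%. One classification can therefore decide whether the threshold is met.

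**4. PFS, as an illustration only**

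The plan gives no PFS assumption to reproduce. Inputs:

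- Base median m: 2.8 months (time to progression in triple-negative patients, 2.1) or 5.7 months (a PARP-inhibitor cohort, 2.2). Neither is a design assumption of this trial.
- Share of patients on bisphosphonates, b: 25–75%. Assumed; not in the documents.
- Share of users' event hazard that is new bone-only disease, f: 10–30%. Assumed; not in the documents.

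With exponential times, the literal rule gives S(t) = (1 − b)·2^(−t/m) + b·2^(−(1−f)t/m).

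- Median in users, m/(1 − f), for m = 2.8: 2.8/0.9 = 3.11, 2.8/0.8 = 3.50, 2.8/0.7 = 4.00 months.
- Overall median, solving S(t) = 0.5: 2.87 to 3.65 months for m = 2.8, and 5.85 to 7.42 months for m = 5.7.
- Share of patients with a later time, b × f: 0.25 × 0.10 = 2.5% to 0.75 × 0.30 = 22.5%, or 0.5 to 4.5 of 20 patients on average.

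**5. The same illustration on the 8-week scan schedule**

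If progression is recorded only at scans, the recorded median is the first scan at which S falls to 0.5 or below. Week 16 is 112/30.44 = 3.68 months.

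- m = 2.8, nothing ignored: S(week 8) = 0.634 and S(week 16) = 2^(−3.68/2.8) = 0.402. The median is recorded at week 16.
- m = 2.8, b = 75%, f = 30%: S(week 16) = 0.25 × 0.402 + 0.75 × 2^(−0.7×3.68/2.8) = 0.101 + 0.396 = 0.497. Still week 16.
- m = 2.8, b = 40%, f = 60% (outside the range above): S(week 16) = 0.6 × 0.402 + 0.4 × 2^(−0.4×3.68/2.8) = 0.241 + 0.278 = 0.519. The median moves to week 24.
- Same b and f, but each ignored event is replaced by the sum of two independent waiting times: with x = ln 2 × 3.68/2.8 = 0.911, S(week 16) = 0.76 × 0.402 + 0.24 × 0.402 × (1 + 0.911) = 0.490. Week 16 again.
- m = 5.7: S(week 24) = 0.511 and S(week 32) = 0.409 with nothing ignored, so the median is at week 32. With b = 75% and f = 30%, S(week 32) = 0.503 and it moves to week 40. The other eight combinations of b and f stay at week 32.

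Whether the recorded median moves therefore depends on inputs and a model that the documents do not supply.

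**6. Sampling error**

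With 20 uncensored exponential times and a true median of 2.8 months, the sample median has a 95% range of about 1.4 to 4.9 months. That is wider than any shift in step 4 for the same base.

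**The case against.** The strongest reply is that the sentence in 4.1 and 6.2 is a deliberate trial-specific rule set beside generic response criteria, and a specific rule may modify a general one. On that reading there is a gap in precedence, not an error. This is fair as a description of the drafting, but it does not remove the problem: if 6.2 governs, a new bone metastasis in a user is not a PFS event. Nor does it help to suppose that only existing lesions were meant. The text does not say so, and 6.7.3.2 would still count unequivocal progression of existing non-target bone lesions.

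It is also fair that the consequence is limited. PFS and ORR are secondary and descriptive, PFS has no decision threshold, and every patient must have measurable disease, so other lesions and death still generate events.

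A reader might infer more than the documents support:

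- **That median PFS is overstated by a definite percentage.** The documents give neither the share of users nor the rate of bone-only progression, and the scan schedule can absorb the shift.
- **That bisphosphonate users are the patients most likely to progress in bone.** No passage says this, and the point does not need it.
- **That counting new bone lesions needs no extra imaging.** Section 6.2.2 describes staging as "studies contributing to response evaluation, e.g. CTs (chest, abdomen, and pelvis), MRI, bone scan, PET, or plain x-rays". Bone scan is one example joined by an *or*, and 6.2.3 repeats only the studies used at baseline.
- **That excluding existing bone lesions from progression is itself a mistake.** It is a debatable choice that the plan makes explicitly.

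**Conclusion.** The conflict is real and nothing in the documents resolves it. For bisphosphonate users, 4.1 and 6.2 remove events that 6.7.3–6.7.4 count, and the PFS and ORR definitions do not say which applies. The direction is certain: if the literal rule is used, PFS is the same or longer and ORR the same or higher. For ORR, each affected patient is worth 5 percentage points at N = 20, next to a 30% threshold. For PFS, the size cannot be derived; the illustrated medians rest on assumed inputs and exponential times, and under 8-weekly scans the recorded median may not change. The primary safety endpoint is not directly affected. The correction is worth making because it is cheap and removes a one-directional bias.

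**What to change.** Reconcile the sentence in 4.1 and 6.2 with 6.7.3–6.7.4, and state that one rule governs the PFS and ORR analyses. For those endpoints:

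- limit the bisphosphonate restriction to bone lesions present at baseline, so that new bone lesions are classified under 6.7.3–6.7.4;
- state whether unequivocal progression of existing bone lesions counts as progression in users;
- state how bisphosphonates started on study are handled.

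Because progression also takes a patient off study (6.2) and off therapy (4.3), the sponsor must decide the consequence for stopping treatment and word those sections consistently. This point concerns only how the endpoints are defined.

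The cost is a wording change in two places. Recorded PFS and ORR may be slightly less favourable. If the sponsor wants new bone lesions detected uniformly, bone imaging would need its own statement, since the current list does not require it.

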6.2.1 Study Entry

Principal investigator will hold the IND for the trial. All patients must be registered with the Clinical Trials Network and Monitoring Office of the UAB Comprehensive Cancer Center ([name], O.C.N.) before enrollment in study. Prior to initiation of therapy eligibility criteria must be confirmed. At the time of registration, a study identification number will be generated. All subsequent case report forms will use this study identification number.

6.2.2 Pre-study Assessments

Informed consent will be obtained before study-specific screening evaluations are performed. Screening evaluations must be performed within 4 weeks prior to day 0.

Within the 4 weeks prior to therapy initiation patients will undergo baseline clinical evaluation (including history, physical evaluation, vital signs, and performance status) and all enrolled patients will undergo biopsy of a selected lesion according to the guidelines described in eligibility criteria. Additional pre-study evaluations include: CBC with differential and platelets, CMP (fasting), CA27.29, pregnancy test (within 7 days if indicated), tumor measurements by images or staging studies which are defined as studies contributing to response evaluation, e.g. CTs (chest, abdomen, and pelvis), MRI, bone scan, PET, or plain x-rays, EKG and echocardiogram, and concomitant medication assessment. The ejection fraction will be confirmed as normal before proceeding with the first dose of lapatinib.

Patients with reasonably accessible lesions as described above, who will not agree with the biopsy, will not be enrolled in the trial. Patients with NO reasonably accessible lesions as described above can be enrolled in the trial.

